4.2. General Statistical Methods and Data Handling

4.2.1. General Methods

All output will be incorporated into Microsoft Excel or Word files, sorted and labeled according to the International Conference on Harmonisation (ICH) recommendations, and formatted to the appropriate page size(s).

Tabulations will be produced for appropriate demographic, baseline, efficacy, and safety parameters. Baseline is considered to be the last assessment prior to first dose. For categorical variables, summary tabulations of the number and percentage within each category (with a category for missing data) of the parameter will be presented. For continuous variables, the mean, median, standard deviation, minimum and maximum values will be presented.

Formal statistical hypothesis testing will be performed on the VAS scores, Total MGD score, eyelid margin vascularity, LGS grade, conjunctival hyperemia, Schirmer score, TBUT, FCS, and OSDI with all tests conducted at the 2-sided, 0.05 level of significance. Summary statistics will be presented, as well as confidence intervals on selected parameters, as described in the sections below.

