A study eye/eyelid is eligible if Inclusion Criteria #3, Inclusion Criteria #5, and Exclusion Criteria #3 are met for the same eyelid at Visit 1 and Visit 2.

Inclusion Criteria #3: Have a clinical diagnosis of moderate to severe MGD and who meet both of the following criteria, in at least one qualifying eyelid (upper and lower eyelid for each eye will be evaluated independently), at both Visit 1 (Screening) and again in the same eye/eyelid at Visit 2 (Randomization) examinations:

Sponsor:	AxeroVision, Inc.		
Protocol:	AXR201901		
Document Version No.:	1.1	Document Date:	26-OCT-2020

- a) Total MGD Score ≥ 5 and ≤ 14 (the sum of the individual score of 5 central glands on the upper and lower eyelids will be evaluated, each will be scored from 0-3: 0 = clear/slightly yellow, 1 = opaque/yellow, whitish, particulate, 2 = paste, 3 = none/occluded; total score will range from 0-15).
- b) Clinical sign severity score of at least 2 (moderate) on vascularity of the eyelid margin

Inclusion Criteria #5: Meet the following criteria, in both or the same qualifying eye as in Inclusion #3, at both Visit 1 (Screening) and Visit 2 (Randomization) examinations:

- a) tFCS score ≥ 3 and ≤ 14 in the NEI/Industry Workshop scale (0-15)
- b) Schirmer score of >7 mm without topical anesthesia

Exclusion Criteria #3: In the study eyelid, have greater than 4 glands that are not expressible from the 5 upper and/or 5 lower eyelid meibomian glands at both Visit 1 and Visit 2.

Least squares means for each treatment group and for the differences between 0.2% AXR-270 Cream and Vehicle, 2.0% AXR-270 Cream and Vehicle, and 0.2% AXR-270 Cream and 2.0% AXR-270 Cream will be presented from each model together with two-sided p-values and 95% confidence intervals at each post-baseline visit. The differences between Day 8 and baseline, Day 15 and baseline, and Day 22 and baseline for each treatment individually will also be presented from the model with two-sided p-values and 95% confidence intervals at each post-baseline visit.

Sample SAS longitudinal model code:

```

PROC MIXED DATA=INDATA;
  BY <EYE> <PARAMETER>; ** include <EYE> as applicable;
  CLASS <TREATMENT> <SUBJECT> <VISIT>;
  MODEL <ENDPOINT>=<TREATMENT> <VISIT> <TREATMENT>*<VISIT> <BASELINE>;
  REPEATED <VISIT> / SUBJECT=<SUBJECT> TYPE=UN;
  RANDOM Intercept;
  LSMEANS <TREATMENT>*<VISIT> / CL ALPHA=0.05;
  ESTIMATE '2.0 - Vehicle @ Day 8' <TREATMENT> -1 0 1
           <TREATMENT>*<VISIT> -1 0 0 0 0 0 1 0 0 /

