           CL ALPHA=0.05;
  ESTIMATE '0.2 - Vehicle @ Day 8' <TREATMENT> -1 1 0
           <TREATMENT>*<VISIT> -1 0 0 1 0 0 0 0 0 /
           CL ALPHA=0.05;
  ESTIMATE '2.0 - 0.2 @ Day 8' <TREATMENT> 0 -1 1
           <TREATMENT>*<VISIT> 0 0 0 -1 0 0 1 0 0 / CL
           ALPHA=0.05;
  ESTIMATE 'Day 8 - Baseline for 2.0' <TIME> -1 0 1
           <TREATMENT>*<TIME> -1 0 1 0 0 0 0 0 0 /
           CL ALPHA=0.05;
RUN;

```

Sponsor:	AxeroVision, Inc.		
Protocol:	AXR201901		
Document Version No.:	1.1	Document Date:	26-OCT-2020

Where <TREATMENT> is sorted in ascending order of 0.2% AXR-270, 2.0% AXR-270, then Vehicle and <VISIT> is sorted in ascending order of Day 8, Day 15, and Day 22.

The variance-covariance structure (TYPE=) will be unstructured (UN). In the event that UN does not converge, then autoregressive (AR(1)) and compound symmetry (CS) will be used in that order until the model converges. A random subject intercept will also be included in the model (using Random INT statement in Proc mixed). An additional BY statement for eye will be added for endpoints that are evaluated by study/non-study eye.

Analysis of the non-study eye/eyelids will also be conducted on each of the above endpoints as supportive analysis.

If any values are missing for the study eye/eyelid, a sensitivity analysis will be conducted where missing values are imputed with the LOCF method.

In addition, time to resolution and responder analysis will be performed for the following efficacy variables:

- Eye Discomfort VAS (6 responder levels)
 - 20%, 30%, 50%, and 100% improvement
 - 10+ points and 15+ points improvement
- Eye Dryness VAS (6 responder levels)
 - 20%, 30%, 50%, and 100% improvement
 - 10+ points and 15+ points improvement
- Study Eyelid Total MGD (2 responder levels)
 - 0 Score
 - 3+ points improvement
- Study Eyelid Margin Vascularity (1 responder level)
 - 1+ step improvement
 - 2+ step improvement
- Study Eye TBUT (2 responder levels)
 - ≥7 seconds
 - ≥10 seconds
- Study Eye LGS Score (2 responder levels)
 - 0 Score
 - 3+ step improvement
- Study Eye tFCS (2 responder levels)
 - 0 Score
 - 3+ step improvement
- Study Eye FCS Central Zone (2 responder levels)
 - 0 Score
 - 1+ step improvement
- Study Eye FCS Inferior Zone (2 responder levels)
 - 0 Score

Sponsor:	AxeroVision, Inc.		
Protocol:	AXR201901		
Document Version No.:	1.1	Document Date:	26-OCT-2020

- 1+ step improvement
- Study Eye FCS Nasal Zone (2 responder levels)
 - 0 Score
 - 1+ step improvement

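### The efficacy model adds a random intercept that is redundant beside the unstructured covariance, and the sample code fits a different intercept from the one the text describes

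*SAP*

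**What the plan says.** SAP 4.6 (Efficacy Evaluation) analyses change from baseline in the continuous endpoints with one longitudinal model, fitted separately by parameter and, where relevant, by eye. The fixed part of the sample code is "MODEL <ENDPOINT>=<TREATMENT> <VISIT> <TREATMENT>*<VISIT> <BASELINE>". The visit factor has three levels: "<VISIT> is sorted in ascending order of Day 8, Day 15, and Day 22".

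For the within-subject covariance the code has "REPEATED <VISIT> / SUBJECT=<SUBJECT> TYPE=UN", and the text agrees: "The variance-covariance structure (TYPE=) will be unstructured (UN". The code then adds the line "RANDOM Intercept", with no `SUBJECT=` option. The text describes that term as a subject-level effect: "A random subject intercept will also be included in the model (using Random INT statement in Proc mixed".

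The fallback rule is: "In the event that UN does not converge, then autoregressive (AR(1)) and compound symmetry (CS) will be used in that order". Nothing says the intercept is dropped under any of the three structures. No fallback allows the variance to differ by visit.

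SAP 4.6 promises from this model the least squares means by arm, the pairwise arm differences and the within-arm changes from baseline, each with p-values and 95% intervals. SAP 4.2.1 has "all tests conducted at the 2-sided, 0.05 level of significance".

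**The concern.** An unstructured matrix and a random subject intercept describe the same thing twice. The intercept adds one constant to every entry of the covariance matrix, and the unstructured matrix can absorb that constant exactly. The likelihood is therefore flat along one direction.

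The fallback rule responds only to non-convergence and cannot tell a specification fault from a data problem. If the redundant parameter causes the flag, the endpoint moves to AR(1), which imposes one common variance at Day 8, 15 and 22. The fit is run endpoint by endpoint, so the covariance structure could differ between endpoints for no reason in the data. Day 22 standard errors could then be off wherever the spread of change differs between visits.

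The printed code has a different fault. Without `SUBJECT=` it specifies one random intercept for the whole data set, which is confounded with the fixed intercept. A programmer has to choose between the text and the code, and the choice affects the within-arm results.

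**Working it through.** **Inputs.** From SAP 4.6: three post-baseline visits, the three covariance structures and the random intercept. From SAP 2.1 and 4.2.3: about 42 subjects per arm, with Vehicle pooled across cohorts. Neither document gives SDs or correlations, and neither has a sample size calculation (SAP 4.1, Protocol 9.6). The SDs and the correlation of 0.6 below are therefore assumptions.

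**1. Parameter count, intercept as in the text.** The marginal covariance is V = σ_b²·J + R, where J is the 3 × 3 matrix of ones. V has 3 × 4 / 2 = 6 distinct entries. The rank of the map from the parameters to those entries is:

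| Structure | Parameters | Rank |
|---|---|---|
| UN alone | 6 | 6 |
| UN + intercept | 7 | 6 |
| AR(1) + intercept | 3 | 3 |
| CS + intercept | 3 | 2 |

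The first and last steps of the ladder are over-parameterised. Only AR(1) plus intercept is identified.

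**2. What the redundancy does to the answer.** On one simulated data set (3 arms × 42, complete data), −2 REML log-likelihood was 376.0245 at σ_b² = 0, 0.1, 0.3, 0.5 and 0.7, and the Day 22 standard error of the arm difference was 0.2867 each time. On the scale of SDs 18/20/22 with exchangeable correlation 0.6, every σ_b² from 0 up to 1/(1'V⁻¹1) ≈ 279 fits equally well. So the split between σ_b² and R is undetermined, but V and the arm contrasts are not.

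**3. Can it raise a flag?** In 60 simulated data sets a general quasi-Newton optimiser reported non-convergence in 17 with the intercept and in 1 without it. The contrast standard errors agreed to within 1e-7. This was not PROC MIXED, and the two fits did not share starting values. It shows that a flag is possible, not how often SAS would raise one.

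**4. What AR(1) then does.** With or without an intercept, AR(1) has a single variance for all visits, estimated near the mean of the three visit variances. Approximately, SE ratio at a visit = √(mean visit variance) / SD at that visit.

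- SDs 18/20/22: √((324 + 400 + 484)/3) = 20.07; 20.07/22 = 0.912, about 9% too small.
- SDs 15/20/25: √((225 + 400 + 625)/3) = 20.41; 20.41/25 = 0.816, about 18% too small.
- The same SDs falling: 20.07/18 = 1.115 and 20.41/15 = 1.361, so too large.
- Equal SDs: ratio 1.

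Simulation of the nominal two-sided 5% test (5,000 runs per row, 42 against 42, AR(1) correlation 0.6):

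| SD at Day 8/15/22 | SE ratio, Day 22 | Type I error, Day 22, AR(1) + intercept | Day 22, UN alone | Day 8, AR(1) + intercept |
|---|---|---|---|---|
| 1/1/1 | 1.00 | 4.5% | 4.6% | 4.7% |
| 1/1.1/1.2 | 0.92 | 6.4% | 4.5% | 3.3% |
| 1/1.25/1.5 | 0.85 | 10.3% | 5.1% | 1.3% |
| 1/1.5/2 | 0.78 | 12.3% | 4.8% | 0.3% |
| 1.5/1.25/1 | 1.27 | 1.3% | 4.8% | 9.6% |

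**5. The intercept as coded.** Without `SUBJECT=`, one random constant with variance τ² is added to all observations. REML cannot see it: with SDs 18/20/22, −2 REML was 2442.43534 at τ² = 0, 4, 25 and 100. It cancels from arm differences, whose Day 22 standard error stays at √(2 × 484/42) = 4.80. It does not cancel from a single arm's mean, whose standard error is √(484/42 + τ²):

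| τ² | 0 | 4 | 25 | 100 |
|---|---|---|---|---|
| Within-arm Day 22 SE | 3.40 | 3.94 | 6.04 | 10.56 |

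The response is change from baseline and the visit factor has no baseline level, so I take the within-arm change to be the least squares mean at that visit. The printed within-arm `ESTIMATE` line instead contrasts levels of a `TIME` variable that is not in the `MODEL` statement. A pure difference between visits would cancel the intercept, but it would not be a change from baseline.

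**The case against.** Much of the opposing case stands.

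- A reader might infer that the model cannot be estimated. That is too strong. Under the text's version only the split between intercept variance and residual matrix is undetermined. The reported quantities are estimable and match the unstructured model if the software stops normally.
- A reader might infer that the efficacy standard errors will be wrong. The documents do not support that. A flat likelihood is not the same as non-convergence, and no flag rate for PROC MIXED has been shown. Even after a fallback, the error needs visit variances that differ, and no SDs are given. A separate check with equal SDs of 20 and correlation 0.6 (2,500 runs) gave 4.9% type I error at Day 22.
- The two faults are alternatives. As printed, the code has no subject intercept, so the 7-for-6 count applies to the text only. The code's redundancy is with the fixed intercept and leaves arm differences alone.
- This is not the only source of efficacy p-values. SAP 4.6 also has chi-squared responder tests and t-tests of time to resolution.
- Safety and tolerability are the primary objective and do not use this model. Both documents treat efficacy as exploratory, and Protocol 9.7 makes p-values descriptive.
- Prespecifying AR(1) and then CS is not in itself an error.

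These points limit the size of the problem. They do not rescue the specification: the intercept adds nothing beside an unstructured matrix, the same fault recurs at the last fallback, and text and code disagree.

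**Conclusion.** The specification is wrong as written and should be fixed, but it does not threaten the trial's primary objective. Three findings are firm because they follow from the algebra: 7 parameters for 6 quantities under UN plus subject intercept, 3 for 2 under CS plus subject intercept, and a coded intercept that contradicts the text and is confounded with the fixed intercept.

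Harm to the arm comparisons is conditional. It needs a non-convergence flag caused by the redundancy and then unequal spread between visits. If both occur, the Day 22 standard error is about 9% too small for SDs 18/20/22 and 18% too small for 15/20/25. It is too large if spread falls, and correct if the SDs are equal. Those SDs are assumptions.

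Harm to the within-arm standard errors arises only if the code is run as printed. It needs no fallback, but its size depends on whatever value the software returns for a variance the data do not inform; a returned value of zero does no harm.

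The reach is limited to exploratory efficacy p-values, confidence intervals and the significance asterisks on the change-from-baseline figures.

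**What to change.** Delete the `RANDOM` statement from the sample code and the sentence on the random subject intercept from SAP 4.6. Keep the `REPEATED` statement by visit within subject with `TYPE=UN`. That alone resolves the redundancy and the conflict between text and code. In the 5,000-run simulations, UN alone gave type I error of 4.5% to 5.1% at Day 22 and 5.0% to 5.5% at Day 8 across all five SD patterns.

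Preferably, also replace the fallbacks with structures that allow a different variance at each visit, for example ARH(1) and then CSH, again without a `RANDOM` statement. `DDFM=KR` is a reasonable option but not needed to correct the fault.

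The necessary change costs one sentence and one line of code; the preferred fallbacks cost one further sentence. No data, visits or subjects are affected. It should be made before unmasking, so that no covariance structure is chosen with treatment results in view.

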4.2.8. Missing, Unused, and Spurious Data

Any missing, unused, or spurious data will be noted in the final CSR. The data will be analyzed as recorded on the CRF. The last observation carried forward (LOCF) approach will be used to analyze incomplete datasets.

All data recorded on the CRF will be included in data listings that will accompany the clinical study report.

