4.4. Subject Disposition

Subject disposition will be tabulated by treatment group, including the number screened overall, the number and percent randomized, the number and percent dosed with 0.2% AXR-270 Cream, the number and percent dosed with 2.0% AXR-270 Cream, the number and percent dosed with Vehicle, the

Sponsor:	AxeroVision, Inc.		
Protocol:	AXR201901		
Document Version No.:	1.1	Document Date:	26-OCT-2020

number and percent that completed the treatment, the number and percent that discontinued treatment and the reasons for discontinuation, the number and percent that completed the study, the number and percent that discontinued prior to completing the study and the reasons for discontinuation, and the number in each subject population for analysis.

A summary will be provided for investigator enrollment by country, study center, and investigator name(s) by treatment dose and overall.

A by-subject listing of study completion information, including the reason for premature treatment and/or study discontinuation, if applicable, will be presented.

4.5. **Demographic and Baseline Characteristics**

Baseline and demographic information will be summarized for the FAS, PPS, and SAF using descriptive statistics by treatment group. Medical history will be summarized for the FAS by treatment group, where medical history includes systemic surgical, ocular surgical, systemic non-surgical, and ocular non-surgical history summarized separately by treatment group. No formal statistical comparisons will be performed.

Baseline, demographic, and medical history data will be provided in data listings.

4.6. **Efficacy Evaluation**

Efficacy analysis will be conducted using the FAS and PPS as outlined below.

All efficacy endpoints are exploratory in nature. The following endpoints will be considered to assess the efficacy of AXR-270 Cream on the study eye/eyelid.

1. Change from baseline in the following individual subject-reported symptoms using VAS (0-100 point scale) in the AXR-270 Cream (0.2% or 2.0%) arms compared to Vehicle at Day 22:
 - Eye Discomfort
 - Eye Dryness
2. Change from baseline in Investigator-related signs of MGD using individual severity scores in AXR-270 Cream arms compared to Vehicle at Day 22:

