- Study Eye FCS Superior Zone (2 responder levels)
 - 0 Score
 - 1+ step improvement
- Study Eye FCS Temporal Zone (2 responder levels)
 - 0 Score
 - 1+ step improvement
- Study Eye Bulbar Conjunctival Hyperemia (2 responder levels)
 - 0 Score
 - 1+ step improvement
- OSDI (1 responder level)
 - <13 Score
- Study Eye Unanesthetized Schirmer Test (1 responder level)
 - >14 mm

Improvement as mentioned above means reduction in score.

Time to resolution will be defined as the duration between the date that a subject’s study eye/eyelid or subject, as appropriate per the endpoint (see Section 2.5.1), reaches a predefined “resolution” value post-baseline and the date of the first dose of study drug, i.e., (date of response – date of first dose) + 1. Time to resolution will be summarized by treatment. The differences, 95% CIs, and p-values, assuming equal variance (pooled), from a two-sample t-test will be provided for 0.2% AXR-270 vs Vehicle, 2.0% AXR-270 vs Vehicle, and 2.0% AXR-270 vs 0.2% AXR-270.

Counts and percentages of subjects/eyes that respond will be presented by treatment. P-values from a chi-squared test will be provided for 0.2% AXR-270 vs Vehicle, 2.0% AXR-270 vs Vehicle, and 2.0% AXR-270 vs 0.2% AXR-270.

By subject listings will be provided for each of the efficacy variables.

Change from baseline figures will be presented for the following:

- Eye discomfort VAS
- Eye dryness VAS
- Total MGD Score
- Vascularity of the eyelid margin
- Upper lid LGS
- tFCS
- Bulbar conjunctiva Hyperemia
- OSDI
- Modified BLISS
- Unanesthetized Schirmer Test

Sponsor:	AxeroVision, Inc.		
Protocol:	AXR201901		
Document Version No.:	1.1	Document Date:	26-OCT-2020

- IOP

The mean change from baseline by treatment will be plotted along the y-axis and visit along the x-axis. Standard deviation bars will be presented along with an asterisk (*) above or below the bars to indicate whether there is significance at an $\alpha=0.05$ level for the treatment compared to vehicle.

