5. CHANGES TO PLANNED ANALYSES

The following analyses are provided in the SAP but not planned in the protocol:

- Responder analysis in Section 4.6
- Time to resolution analysis in Section 4.6
- Additional evaluation of the difference between 2.0% AXR-270 Cream and 0.2% AXR-270 Cream at each post-baseline visit
- Additional evaluation of the within treatment change-from-baseline difference at each post-baseline visit

Sponsor:	AxeroVision, Inc.		
Protocol:	AXR201901		
Document Version No.:	1.1	Document Date:	26-OCT-2020

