14.2.5.3	Sensitivity Analysis of Tear Break-Up Time (sec) Actual Values and Changes Over Time by Study/Non-study Eye – Full Analysis Set
14.2.6.1*	Upper Lid LGS Actual Values and Changes Over Time by Study/Non-study Eye – Full Analysis Set
14.2.6.2	Upper Lid LGS Actual Values and Changes Over Time by Study/Non-study Eye – Per Protocol Set
14.2.6.3	Sensitivity Analysis of Upper Lid LGS Actual Values and Changes Over Time by Study/Non-study Eye – Full Analysis Set
14.2.7.1*	tFCS Actual Values and Changes Over Time by Study/Non-study Eye – Full Analysis Set
14.2.7.2	tFCS Actual Values and Changes Over Time by Study/Non-study Eye – Per Protocol Set
14.2.7.3	Sensitivity Analysis of tFCS Actual Values and Changes Over Time by Study/Non-study Eye – Full Analysis Set
14.2.8.1	Individual Region FCS Actual Values and Changes Over Time by Study/Non-study Eye – Full Analysis Set
14.2.8.2	Individual Region FCS Actual Values and Changes Over Time by Study/Non-study Eye – Per Protocol Set
14.2.8.3	Sensitivity Analysis of Individual Region FCS Actual Values and Changes Over Time by Study/Non-study Eye – Full Analysis Set
14.2.9.1*	Bulbar Conjunctival Hyperemia Actual Values and Changes Over Time by Study/Non-study Eye – Full Analysis Set
14.2.9.2	Bulbar Conjunctival Hyperemia Actual Values and Changes Over Time by Study/Non-study Eye – Per Protocol Set
14.2.9.3	Sensitivity Analysis of Bulbar Conjunctival Hyperemia Actual Values and Changes Over Time by Study/Non-study Eye – Full Analysis Set
14.2.10.1*	OSDI Score Actual Values and Changes Over Time – Full Analysis Set
14.2.10.2	OSDI Score Actual Values and Changes Over Time – Per Protocol Set
14.2.10.3	Sensitivity Analysis of OSDI Score Actual Values and Changes Over Time – Full Analysis Set
14.2.11.1*	Modified BLISS at each Visit – Full Analysis Set
14.2.11.2	Modified BLISS at each Visit – Per Protocol Set
14.2.11.3	Modified BLISS Shifts from Baseline Over Time – Full Analysis Set
14.2.11.4	Modified BLISS Shifts from Baseline Over Time – Per Protocol Set
14.2.12.1*	Unanesthetized Schirmer Actual Values and Changes Over Time by Study/Non-study Eye – Full Analysis Set
14.2.12.2	Unanesthetized Schirmer Actual Values and Changes Over Time by Study/Non-study Eye – Per Protocol Set
14.2.12.3	Sensitivity Analysis of Unanesthetized Schirmer Actual Values and Changes Over Time by Study/Non-study Eye – Full Analysis Set
14.2.13	Time to Resolution – Full Analysis Set
14.2.14	Responder Analysis – Full Analysis Set

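### Time to resolution is compared by a t-test that only resolvers can enter, and ten of the 36 responder levels can already be met at baseline

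*SAP*

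**What the plan says.** SAP section 4.6 defines time to resolution from the date on which the subject, eye or eyelid reaches a predefined resolution value after baseline, calculated as "date of response – date of first dose) + 1". For the three pairs of arms, "The differences, 95% CIs, and p-values, assuming equal variance (pooled), from a two-sample t-test will be provided". The companion responder analysis uses counts and percentages: "P-values from a chi-squared test will be provided for 0.2% AXR-270 vs Vehicle", and likewise for the other two pairs.

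The output in SAP section 7.1 is Table 14.2.13, "Time to Resolution – Full Analysis Set". Section 3.1 defines that set as all randomised subjects. On incomplete data, section 4.2.8 says: "The last observation carried forward (LOCF) approach will be used to analyze incomplete datasets".

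On status, section 4.6 states: "All efficacy endpoints are exploratory in nature". Section 5 lists "Time to resolution analysis in Section 4.6" among the analyses added to those in the protocol. Table 14.2.13 carries no topline asterisk, and protocol section 9.7 treats p-values as descriptive.

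The responder levels in section 4.6 mix changes from baseline with absolute thresholds. An example of the second kind is "Study Eye Unanesthetized Schirmer Test (1 responder level"), set at >14 mm.

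**The concern.** A subject who never reaches the level has no date of response and so no value for this variable. Sections 4.2.7, 4.2.8, 4.6, 5 and 7 of the SAP and section 9 of the protocol contain no censoring rule, substitute value or time-to-event method. LOCF carries scores forward; it cannot create a response date for someone observed not to respond. The t-test can therefore use resolvers only, and resolving is an outcome that treatment is meant to change. If treatment works mainly by making more subjects resolve, the test hardly sees it. If the additional active resolvers resolve late, they lengthen the active mean and the test can favour Vehicle. Tables 14.2.13 and 14.2.14 could then point in opposite directions, with no rule for reading them together.

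The second issue is the absolute thresholds. The SAP does not say whether a subject already at the threshold at baseline can *reach* it afterwards, and nothing removes such a subject. Anyone who starts at target and stays there can count as a responder without changing.

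**Working it through.** **Inputs.** From the documents: about 42 subjects per active arm and 42 pooled Vehicle subjects (SAP 2.1, 4.2.3); post-baseline visits at Days 8, 15 and 22; two-sided 0.05, the level section 4.2.1 gives for the formal tests. There is no sample size or power figure to reproduce. All resolution rates below are assumptions. A responder is taken as resolved at any visit up to Day 22, since the SAP names no visit.

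**Worked case, reversal.** Of 42 per arm, active resolves 6/6/12 at Days 8/15/22 (24 in all) and Vehicle 6/2/2 (10 in all). Active has at least as many resolvers at every visit.

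- Resolver means: active (6×8 + 6×15 + 12×22)/24 = 402/24 = 16.75 days; Vehicle (6×8 + 2×15 + 2×22)/10 = 122/10 = 12.20 days. Active looks 4.55 days slower.
- Pooled t-test: within-arm sums of squares 808.5 and 313.6, pooled variance 1122.1/32 = 35.07, standard error √[35.07 × (1/24 + 1/10)] = 2.23, t = 2.04 on 32 df, p = 0.0495.
- Chi-squared on 24/42 v 10/42: 84 × (24×32 − 10×18)² / (34×50×42×42) = 9.69, p = 0.002, favouring active.
- Log-rank: observed minus expected for active is 0 + 2 + 5.44 = 7.44; variance 2.60 + 1.80 + 2.77 = 7.17; statistic 7.71, p = 0.005, favouring active.

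**Worked case, blindness.** Active resolves 12/9/6 (27 of 42) and Vehicle 4/3/2 (9 of 42). Both resolver means are 13.4 days (363/27 and 121/9), so the t-test gives a difference of 0 and p = 1.00. Chi-squared gives p = 0.00007 and log-rank p = 0.00008.

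**Simulation.** 20,000 trials per scenario, 42 per arm: pooled t-test on resolvers, discrete log-rank on all subjects, uncorrected chi-squared on proportions. For constant hazards, the proportion resolved is 1 − (1 − h)³; for example 1 − 0.7³ = 66% and 1 − 0.9³ = 27%. Scenarios (c) to (f) give the percentage of each arm resolving at Days 8/15/22.

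| Scenario (active v Vehicle) | Resolved | t-test significant | Log-rank | Chi-squared |
|---|---|---|---|---|
| (a) weekly hazard 0.3 v 0.1 | 66% v 27% | 9% | 96% | 96% |
| (b) weekly hazard 0.4 v 0.2 | 78% v 49% | 13% | 85% | 83% |
| (c) 10/10/40 v 10/5/5 | 60% v 20% | 61% for Vehicle | 93% | 98% |
| (d) 10/15/30 v 10/8/7 | 55% v 25% | 35% for Vehicle | 72% | 83% |
| (e) 10/15/20 v 10/5/5 | 45% v 20% | 28% for Vehicle | 63% | 70% |
| (f) 40/15/5 v 10/15/35 | 60% v 60% | 99% | 21% | – |
| Null, hazard 0.2 in both | 49% v 49% | 5.0% | 5.1% | – |

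In (a) and (b) the t-test significantly favours Vehicle in under 1% of trials.

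**Count of levels.** As listed: 6 + 6 (VAS) + 2 (MGD) + 2 (vascularity) + 2 (TBUT) + 2 (LGS) + 2 (tFCS) + 10 (five FCS zones) + 2 (hyperemia) + 1 (OSDI) + 1 (Schirmer) = 36. The headings sum to 35 because vascularity is headed as one level but lists two. Thirteen levels are absolute thresholds. Entry criteria rule out three at baseline: MGD 0 (entry ≥5), tFCS 0 (entry ≥3) and OSDI <13 (entry >30). The other ten can already hold: TBUT ≥7 s, TBUT ≥10 s, LGS 0, zero in each of five FCS zones, hyperemia 0, and Schirmer >14 mm (entry >7 mm, no upper limit). For the zones this is certain in some subjects: an eligible tFCS of 3 can involve at most three non-zero zones, so at least two of five are 0; a tFCS of 4 leaves at least one.

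**Dilution.** Assume 40% v 15% response among subjects not at target, and that a proportion b of each arm starts and stays at target and counts as responding. The difference is then (1 − b) × 25 points. Power is from exact binomial enumeration of the uncorrected chi-squared test.

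| Already at target | Difference | Power, all 42 per arm | Power, only those not at target (n per arm) |
|---|---|---|---|
| 0% | 25 points | 75% | 75% (42) |
| 20% | 20 points | 49% | 67% (34) |
| 40% | 15 points | 31% | 53% (25) |

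**The case against.** The strongest defence is that little depends on this test. The primary objective is safety, efficacy is exploratory, and neither the time-to-resolution nor the responder table is topline. The chi-squared test already compares the proportion resolved, and in (a) to (e) log-rank adds little to it. With no treatment effect the t-test holds its size. Where arms differ only in timing, as in (f), it is far more sensitive than log-rank. The reversals need a benefit concentrated late, which no document supports; the corticosteroid study in dry eye described in the protocol introduction reported sign differences as early as Week 2. The worked reversal falls only just below 0.05.

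On the baseline point, *reaches* can be read as requiring a transition. The number of subjects starting at target is unknown. Counting them keeps the randomised denominator and, in expectation, dilutes rather than biases. Seven of the ten levels (LGS, the five zones, hyperemia) have a change-based companion level, and the longitudinal model includes the baseline value. LGS is done only at a subset of sites, so 42 per arm overstates its numbers.

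These points limit the consequence, and each is fair. None supplies a rule for non-resolvers or makes a resolver-only mean difference describe the Full Analysis Set. Losing a real benefit needs no late pattern: it happens under the constant hazards of (a) and (b).

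**Conclusion.** The concern holds and should be fixed. The stated method, applied as written, compares subsets selected after randomisation under a Full Analysis Set label. The fault lies in what is estimated when treatment has an effect, not in false positives when it has none. Under the assumed rates the t-test finds a large benefit in about one trial in ten (9% and 13%) where log-rank finds it in 96% and 85%. With late benefit it significantly favours Vehicle in 28% to 61% of trials.

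That ten of the 36 listed levels can already hold at baseline follows from the lists and entry criteria alone. How much this dilutes the responder comparisons depends on how many subjects start at target, which the documents do not give, and on how *reaches* is programmed.

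No confirmatory conclusion is at risk. The cost is an exploratory table whose p-values can contradict the responder table beside it, and weaker comparisons for the ten levels.

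**What to change.** In SAP section 4.6, replace the t-test with Kaplan-Meier estimates and a log-rank test on all Full Analysis Set subjects, censoring those who do not resolve at their last assessment. With only three scheduled visits, a discrete-time or interval-censored test is equally suitable. If timing among resolvers is of interest, show it descriptively, without a p-value and with the number resolved beside it.

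For the ten absolute-threshold levels, restrict the responder and time-to-resolution risk sets to subjects not at the threshold at baseline, and report that denominator.

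In the same edit, state which listed levels count as resolution values, say at which visit a responder is counted, and correct the vascularity heading from one level to two.

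This needs SAP wording and standard PROC LIFETEST output, with no new data or visits. Two costs should be acknowledged: smaller denominators for the ten levels, and less sensitivity than the t-test when arms differ only in timing (21% v 99% in scenario (f)).
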